Rationale	
Open questions are still needed to be answered:
 
 - In the exclusive radiotherapy scenario, does ENI produce an overall or biochemical relapse free survival advantage over prostate only radiotherapy for intermediate/high/very high-risk cases? - If ADT is added to prostate only radiotherapy, in intermediate/high/very high-risk cases, ENI is any longer needed?

	
 - Is ENI, associated or not to ADT, linked with an OS or bRFS survival advantage in patients submitted to adjuvant postsurgical prostate radiotherapy? - Additional toxicity due to the larger volumes treated might be reduced by more sophisticated radiotherapy techniques when ENI is added to prostate? - How many Radiation Oncology centers use ENI to treat patients with intermediate/high/very high-risk prostate cancer, with or without ADT? - The data obtained from the present observational study will be helpful for designing a subsequent randomized controlled trial.
End-points	
Primary:
 
 - Overall survival; 
Secondary:
 
 - Cause-specific (CSS) and Biochemical Relapse Free survival (bRFS); - acute and late toxicity evaluation (rectal, bladder, bowel toxicity, according to CTCAE v.4 scale); - Quality of Life deterioration (according to the UCLA-PCI scale).
Study design	
This is a prospective, multicenter, observational cohort study aimed to describe the advantage/disadvantage of different treatments of patients with intermediate/high/very high risk prostate cancer, through a web-based database.
 
The study will include all consecutive patients affected by intermediate, high or very high-risk prostate cancer that fit to the inclusion criteria and who are evaluated at each Centre involved in the study. Patients may have already undergone or not to radical prostatectomy and/or pelvic lymphadenectomy.
 
Phase 1: Establishment of the network of Centers involved in the study Phase 2: Activation and recruitment of eligible cases Phase 3: Follow-up (1,3,6,12/18,24/30/36 months)

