Toxicity	NCI Common Terminology Criteria for Adverse Events (CTCAE) version 4 for adverse event (AE) reporting. The CTCAE version 4 is identified and located on the CTEP web site at: http://ctep.cancer.gov/protocolDevelopment/electronic_applications/ctc.htm
Quality of Life	Quality of life and complications due to prostate cancer (Italian UCLA-PCI) General quality of life (SF-12 Standard V1)

Background

The extent of the problem

Prostate cancer (PCa) is the most common male malignancy in the United States and the rest of the Western world and its incidence is rising also in Asia, causing some concerns for public health [1, 2]. In Italy prostate cancer is in the third place of the cancer mortality scale (8% of all cancer related deaths) even if a constant, though moderate, annual decrease (-1.8%) has been observed for over twenty years [3] as well as a consequent increase in overall survival [4]. Despite these data, still now, in the post PSA era, current estimates indicate that high-risk disease accounts for 15% of all PCa diagnoses in the United States [5] and even more in the low-PSA screening regions.

Radiotherapy for prostate cancer: some open questions

Several modalities, alone and/or in combination, have been advocated to treat patients with intermediate/high/very high risk PCa [6], but universally accepted consensus guidelines are still lacking. Mounting evidence supports the use of a multimodality approach to treat locally advanced prostate cancer and in particular the combination of Radiation Therapy (RT) with Total Androgenic Deprivation (ADT); adjuvant post-surgical RT is also needed in many cases submitted to radical prostatectomy (RP) because of unexpected extracapsular invasion or microscopically involved margins. In both cases, some issues are still present regarding RT: volumes of interest, total dose, radiation techniques and fractionation.

The efficacy of elective nodal irradiation and the issue of its association with hormonal manipulation in the context of radical exclusive radiotherapy for prostate cancer

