- Treatment : type of treatment, start date, PSA value before treatment; if surgery type of surgery and pathological TNM, margins, Gleason Score, number of positive lymph nodes; if external RT (intent, modality, technique, dose/fraction, volumes, concomitant hormonal therapies); if brachytherapy (type, intent, dose); if hormone therapy (type of drugs, start and end date, total duration);
- Acute and late toxicities;
- Biochemical Relapse with PSA value and date of last PSA;
- Quality of life and symptoms due to prostate cancer (Italian UCLA-PCI);
- General quality of life SF-12.

Toxicity and response evaluation

The enrolled patients will undergo the first follow up visit one month after the end of radiotherapy. On that occasion, clinical examination will be performed and previously prescribed blood tests, if required, will be evaluated. Genitourinary and gastrointestinal toxicity due to radiation therapy for prostate cancer will be reported according to the NCI Common Terminology Criteria for Adverse Events (CTCAE) version 4 for adverse event (AE) reporting. The CTCAE version 4 is identified and located on the CTEP web site at:

http://ctep.cancer.gov/protocolDevelopment/electronic_applications/ctc.htm [48]

In addition, a Case Report Form (CRF) will be completed (see Attachment 2), regarding:

- Technical characteristics of the radiation treatment (dose, volume, technique, association or not with hormonal therapy);
- Quality of life and complications due to prostate cancer (according to Italian UCLA-PCI) [45, 46];
- General quality of life (SF-12 Standard V1) [47].

Thereafter patients will be evaluated at 3-months, 6-months and 12-months after the end of radiotherapy, and then every 6 months for at least 24 months. During all those scheduled follow up visits, PSA level (jointly with testosterone, in case of association with hormonal therapy) and

previously prescribed blood texts if required, will be evaluated. Patients will undergo clinical examination, and genitourinary and gastrointestinal toxicity will be assessed according to the CTCAE v4.0 classification scale). In addition, a CRF (see Attachment 3) will be completed at each visit, regarding:

- Survival status (mortality, date and cause of death) or exit from the study;
- If macroscopical recurrence or disease progression occurred, the radiological exams (if performed);
- Further treatments received/planned after radiotherapy;
- The last available PSA;

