
select (1=G0, 2=G1, 3=G2, 4=G3, 5=G4, 6=Unknown)

Date yyyy-mm-dd

Urinary Acute Toxicity

select (1=G0, 2=G1, 3=G2, 4=G3, 5=G4, 6=Unknown)

Date

Late Toxicity bladder/ rectum

select (1=Yes, 2=No, 3=Unknown)

Date yyyy-mm-dd

Proctitis

select (1=G0, 2=G1, 3=G2, 4=G3, 5=G4, 6=I Unknown)

Date yyyy-mm-dd

Cystitis

select (1=G0, 2=G1, 3=G2, 4=G3, 5=G4, 6= Unknown)

Date yyyy-mm-dd

Impotence

select (1=No, 2=Yes pre RT, 3=Yes post RT, 4= Unknown)

Date yyyy-mm-dd

Incontinence

select (1=No, 2=Yes pre RT, 3=Yes post RT, 4=Unknown)

TABLE 1 – Toxicity

RECTAL/SMALL BOWEL Acute TOX

G0: No Toxicity

G1: Increased alvus frequency not requiring any treatment. Rectal pain or abdominal pain not requiring any painkillers

G2: Diarrhoea, mucositis, rectal pain or abdominal pain requiring painkillers

G3: Diarrhoea requiring parenteral supportive care, severe mucositis or haematological alterations requiring treatment. Abdominal distension

G4: Acute or subacute obstruction, fistula or perforation, haemorrhage requiring blood transfusion. Abdominal pain or tenesmus requiring ileostomy

BLADDER Acute TOX

G0: No Toxicity

G1: Low urinary tract symptoms (LUTS) and dysuria not requiring any treatment

G2: LUTS, dysuria and urgency requiring treatment or anaesthetics

G3: Severe LUTS, urgency, dysuria, pelvic pain or bladder spasms and haematuria

G4: Haematuria requiring blood transfusion, urinary obstruction, ulceration and necrosis

Late TOX PROCTITIS

G0: No Toxicity

G1: Mild rectal pain, Slight diarrhoea (less than 5 discharges). Small bleeding

G2: Diarrhoea (more than 5 discharges). Significant mucosal secretions and intermittent rectal bleeding

G3: Obstruction or haemorrhage requiring surgery

G4: Necrosis, perforation or fistula

Late TOX CYSTITIS

G0: No Toxicity

G1: Slight epithelial atrophy, small telangiectasia, microscopic haematuria

G2: Moderate LUTS, Intermittent macroscopic haematuria

G3: Severe LUTS and dysuria spread of telangiectasia. Frequent haematuria. Reduction in bladder capacity (less than 150 cc)

G4: Necrosis, bladder capacity reduced (less than 100 cc). Severe haemorrhagic cystitis

SF-12 STANDARD ITALIAN VERSION

(Apolone G et al. 2001)

	Excellent	Very good	Good	Fair	Poor
1 In general, you would say that your health condition is:	1	2	3	4	5
The following questions regard some activities you might do during a typical day. Does your health condition actually limit you in doing these activities?					

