
Acute Toxicities

Rectal Acute Toxicity (Grade)		Date Tox.	
Urinary Acute Toxicity (Grade)		Date Tox.	
Small Intestine Acute Toxicity (Grade)		Date Tox.	

GI Acute Toxicity (small bowel)

(see Table 1)

select (1=G0, 2=G1, 3=G2, 4=G3, 5=G4, 6=Unknown)

Date yyyy-mm-dd

Rectal Acute Toxicity

select (1=G0, 2=G1, 3=G2, 4=G3, 5=G4, 6=Unknown)

Date yyyy-mm-dd

Urinary Acute Toxicity

select (1=G0, 2=G1, 3=G2, 4=G3, 5=G4, 6=Unknown)

Date

Late Toxicity bladder/ rectum

select (1=Yes, 2=No, 3=Unknown)

Date yyyy-mm-dd

Proctitis

select (1=G0, 2=G1, 3=G2, 4=G3, 5=G4, 6=I Unknown)

Date yyyy-mm-dd

Cystitis

select (1=G0, 2=G1, 3=G2, 4=G3, 5=G4, 6= Unknown)

Date yyyy-mm-dd

Impotence

select (1=No, 2=Yes pre RT, 3=Yes post RT, 4= Unknown)

Date yyyy-mm-dd

Incontinence

select (1=No, 2=Yes pre RT, 3=Yes post RT, 4=Unknown)

TABLE 1 – Toxicity

RECTAL/SMALL BOWEL Acute TOX

G0: No Toxicity

G1: Increased alvus frequency not requiring any treatment. Rectal pain or abdominal pain not requiring any painkillers

G2: Diarrhoea, mucositis, rectal pain or abdominal pain requiring painkillers

G3: Diarrhoea requiring parenteral supportive care, severe mucositis or haematological alterations requiring treatment. Abdominal distension

G4: Acute or subacute obstruction, fistula or perforation, haemorrhage requiring blood transfusion. Abdominal pain or tenesmus requiring ileostomy

BLADDER Acute TOX

G0: No Toxicity

G1: Low urinary tract symptoms (LUTS) and dysuria not requiring any treatment

G2: LUTS, dysuria and urgency requiring treatment or anaesthetics

G3: Severe LUTS, urgency, dysuria, pelvic pain or bladder spasms and haematuria

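### Toxicity is declared on CTCAE v4, but the follow-up forms grade it on an unsourced, unmapped Table 1 and have no late small-bowel item

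*Combined protocol and SAP*

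**What the plan says.** The protocol names one scale throughout. The synopsis (End-points) lists as a secondary endpoint "acute and late toxicity evaluation (rectal, bladder, bowel toxicity, according to CTCAE v.4 scale". The synopsis row on toxicity and the closing summary under Aims of the study name the same scale. Under Toxicity and response evaluation, toxicity at the 1-month visit "will be reported according to the NCI Common Terminology Criteria for Adverse Events (CTCAE) version 4". For later visits, "genitourinary and gastrointestinal toxicity will be assessed according to the CTCAE v4.0 classification scale".

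The forms supply a different reference. Attachments 2 and 3 both direct the assessor to a Table 1 and print it in full. For acute gastrointestinal toxicity it has a single list, headed "RECTAL/SMALL BOWEL Acute TOX", whose third grade reads "G3: Diarrhoea requiring parenteral supportive care, severe mucositis or haematological alterations requiring treatment. Abdominal distension". For late proctitis the first grade reads "G1: Mild rectal pain, Slight diarrhoea (less than 5 discharges). Small bleeding", and the second grade begins above 5 discharges. The late section of both forms is labelled for bladder and rectum only.

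**The concern.** The endpoint is whatever the forms record. If an assessor grades from the table on the form, the database holds Table 1 grades, and the protocol gives no route from those to CTCAE v4. A report that follows the endpoint definition would then attach the CTCAE name to grades assigned on another text.

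Toxicity matters more here than its secondary status suggests. One of the study's stated questions is whether the added toxicity of treating larger volumes can be reduced. Aim 4 is to register toxicity, Aim 5 to compare it across subgroups and with historical AIRO data, and Aims 6 and 7 to use the results in designing a randomised trial. Each of these needs grades whose scale is known. The background section also says that acute gastrointestinal and genitourinary complications were reported more often with whole-pelvis than with prostate-only treatment, so bowel grading is central to the ENI question.

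**Working it through.** The documents give no toxicity rate, power or sample size, so there is no toxicity figure to reproduce. The plan's only computed figure concerns 5-year survival: 0.8 ± 1.96 × √(0.8 × 0.2 / 400) = 0.8 ± 0.039, or 0.761 to 0.839. This agrees with the stated 0.76–0.84 and does not involve toxicity.

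**Step 1: coverage.** The endpoint has 3 organs × 2 periods = 6 components.

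| Component | Field on the forms | Grade text supplied |
|---|---|---|
| Acute rectal | own grade and date | Table 1, list shared with small bowel |
| Acute small bowel | own grade and date | Table 1, list shared with rectum |
| Acute bladder | own grade and date | Table 1, bladder list |
| Late rectal | proctitis, grade and date | Table 1, late proctitis |
| Late bladder | cystitis, grade and date | Table 1, late cystitis |
| Late bowel | none | none |

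Five of six components rest on Table 1, one has no graded item, and none has a CTCAE field or CTCAE text. Late impotence and incontinence are also recorded, but as yes/no with timing rather than as grades.

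**Step 2: traceability.** The comorbidity scale, SF-12 and UCLA-PCI forms each carry a source line. Table 1 carries none and does not mention CTCAE. The toxicity items ask for a grade and a date, not the criterion that produced the grade. A Table 1 grade therefore cannot be converted at analysis, and an automatic consistency check would not flag it.

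**Step 3: grade boundaries, as printed.**
- Rectal and small-bowel acute grades are entered separately but draw on one list. No rule says how to attribute a shared symptom such as diarrhoea to one site.
- The third acute bowel grade contains a haematological criterion that is not tied to the bowel.
- Late proctitis is grade 1 below 5 discharges and grade 2 above 5. Exactly 5 has no grade.
- Late cystitis grade 1 consists only of mucosal atrophy, small telangiectasia and microscopic blood in urine. Scheduled visits provide clinical examination, PSA (with testosterone if hormones are given) and blood tests if required. None of these is stated to detect those findings.

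**Step 4: direction of any effect.** Let t be the true rate of grade 3 or higher acute bowel toxicity, equal in both groups. Let h be the share of the remaining patients moved to grade 3 by the haematological criterion alone. The observed rate is t + (1 − t) × h. The documents give neither t nor h, so every value below is assumed.

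| t | h with ENI | h without ENI | Observed, ENI | Observed, no ENI | Ratio |
|---|---|---|---|---|---|
| 5% | 2% | 2% | 6.9% | 6.9% | 1.00 |
| 5% | 3% | 1% | 7.9% | 6.0% | 1.32 |
| 5% | 1% | 3% | 6.0% | 7.9% | 0.76 |
| 5% | 5% | 0% | 9.8% | 5.0% | 1.95 |
| 2% | 3% | 1% | 4.9% | 3.0% | 1.66 |
| 2% | 5% | 0% | 6.9% | 2.0% | 3.45 |

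For the second row: 0.05 + 0.95 × 0.03 = 0.0785 and 0.05 + 0.95 × 0.01 = 0.0595. The sign of the shift is set entirely by which group has the larger h. The missing late bowel item could work the other way, by leaving late harm from larger pelvic volumes ungraded.

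**The case against.** The strongest reply is that this is a labelling matter. The text of CTCAE v4 is not in the documents, so a reader might infer that Table 1 is an in-house scale that differs from CTCAE line by line, but that cannot be shown from them. The pointer to Table 1 stands only under the acute small-bowel item, and nothing says that Table 1 replaces CTCAE. This stands. What can be said is that Table 1 is unsourced, unlabelled and unmapped.

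A reader might also infer that the table biases results against ENI. The documents do not support this: they give no rate of haematological events by ENI status, equal rates cancel, and reversed rates favour ENI. The criterion itself may be a translation slip for bleeding. Another item on the pre-treatment form asks for numbers of blood tests where the protocol body lists biopsy samples. The criterion needs clarifying, but it is not established as a blood-count rule.

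A third tempting inference is that small-bowel and rectal toxicity cannot be separated. They have separate grade and date fields, and a physician may be able to attribute symptoms to an organ. Only the criteria are shared.

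Some further points reduce the weight. Bleeding that does not need surgery can be read as late-proctitis grade 2, so no second gap is claimed there. Late cystitis grades 2 to 4 each include a criterion that can be observed clinically, and routine care may supply the findings for grade 1. Attachment 3 repeats the acute small-bowel field and has a tick-box for new gastrointestinal comorbidity, so a late bowel event might be entered in one of them, but only as acute or ungraded. All patients are graded on the same table, and UCLA-PCI records bowel and urinary function independently.

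These points limit the consequences. They do not remove the mismatch between the declared scale and the printed one, or supply a late small-bowel grade.

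**Conclusion.** The point holds as a contradiction within the documents: the endpoint is CTCAE v4, and the forms supply another grading text with no stated link to it. Five of the six components are graded on that text, and late small-bowel toxicity has no graded item. The conclusion assumes that assessors grade from the form in front of them.

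No numerical size can be given, because the documents contain no toxicity rates. The direction of any effect on an ENI versus no-ENI comparison is undetermined. The consequence that can be stated is that grades may be reported as CTCAE v4 when they are not, which limits their use for Aims 4 to 7.

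This should be fixed, but it concerns a secondary endpoint. A reader should not infer that the overall survival endpoint or its sample size is affected.

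**What to change.** Reconcile the endpoint statements (synopsis End-points and Toxicity, the summary under Aims of the study, and Toxicity and response evaluation) with Attachments 2 and 3. The direct route is to put the declared CTCAE v4 terms on the forms, itemised for rectum, small bowel and bladder, and to add a late small-bowel item.

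If Table 1 is kept, the sponsor should:
- name it, with its source, as the endpoint scale wherever CTCAE v4 now stands;
- give separate criteria for rectum and small bowel;
- make the grade boundaries exhaustive;
- record haematological findings separately from bowel grades;
- state how the late cystitis grade 1 findings will be obtained, or revise that grade;
- add the late small-bowel item.

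The clinical thresholds are for the sponsor to decide.

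The cost is a revision of the forms and web database with a note to centres, and no extra visits. If grades have already been entered, they would have to be re-read against source notes. With 400–500 patients at 15–20 centres, that is real work, so the change is cheapest before data entry.

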ATTACHMENT 3 – 3, 6, 9, 12, 18, 24, 36 MONTHS FOLLOW UP

	
1 He does not adhere anymore for health reasons, specify _____
 
2 He is not interested anymore to take part in the study
 
3 He is not traceable

Does the patient still undergo Hormonal Therapy?	
1. Yes
 
If yes: (FILL IN POINT 4 BELOW)
 
0 No
 
If no: Date of ending hormonal therapy  / /  day month year

Has he developed new comorbidities? (It is possible to fill in more than one option)	
0 . No
 
1 . Yes
 
If yes:
 
 1 Cardiac (specify _____) 2 Vascular (including hypertension) 3 Pulmonary (specify _____) 4 Eye, ear, nose, throat, larynx 5 Gastro-intestinal (specify _____) 6 Hepatic (liver only) 7 Renal (kidneys only) 8 Musculo-skeletal (specify _____) 9 Intertegumentary (skin) 10 Neurological (specify _____) 11 Endocrine-metabolic (specify _____) 12 Cognitive-psychiatric, behaviour 13 Genito-urinary (ureter-genitals) (specify _____) 14 Other malignancies (including Haematopoietic malignancies)

	15 Other, specify _____	
Has he undergone further treatments for prostate cancer, subsequent to those reported in Attachment 1 (1-month follow up)?	0 No	
	1 Yes	
	If yes:	
	1	Surgery
	2	External Beam Radiation Therapy
	3	Brachytherapy
	4	Radiometabolic Therapy
	5	Hormonal Therapy
	6	Focal Therapy
7	Chemotherapy	
8	Others, specify _____	

If he has undergone further treatments, specify:

Date of starting the new treatment |__|/|__|/|__|_|_|

day month year

PSA before starting the new treatment |__|_|_|_|. |__|_|_| ng/mL

 External Beam Radiotherapy	
Aim of Radiotherapy	1 Palliative
	2 Other, specify_____
Modality	1 IGRT
	2 Non IGRT
Technique	1 3D-CRT
